**Table 1. Standard deviation and precision**

Standard deviation	Precision
2.2	1.27
2.3	1.33
2.4	1.39
2.5	1.44
2.6	1.5
2.7	1.56

## 7. Statistical Methods

---

### 7.1. Study Subjects

#### 7.1.1. Disposition of Subjects

A disposition of subjects according to their follow-up status at each visit will be provided by randomization group. Reasons for study exit will be summarized over time.

#### 7.1.2. Clinical Investigation Plan Deviations

CIP deviations will be listed and the number of deviations will be summarized by type and overall.

#### 7.1.3. Analysis Sets

The **full analysis subject set** (FAS) includes all subjects who signed the study-specific ICF and enrolled in the study.

The **test subject set** includes all subjects who underwent a lead placement (Tined Lead or Test Stimulation Lead) attempt, whether the procedure was successful or not.

The **randomized subject set** includes all randomized subjects.

The **complete case subject set (CC)** includes the subject set who have data available at baseline and follow-up.

**Screen failures** includes the subject set who enrolled in the study but did not qualify for lead implant or neurostimulator device implant/randomization.

## 7.2. General Methodology

### 7.2.1. General Statistical Considerations

Continuous measures will be reported as N, means, medians, standard deviations, minimums and maximums. All post-randomization data summaries will be provided by randomization group. Categorical measures will be reported in frequency distributions. No hypothesis testing will be performed.

For outcomes examining change from baseline, change ( $\Delta$ ) will be calculated as follow-up scores ( $S_v$ ) minus baseline scores ( $S_0$ ).

$$\Delta = S_v - S_0$$

Percent change will be calculated as 100 times the change divided by the baseline score.

$$\text{Percent change} = 100 * \Delta / S_0$$

Data analysis will be performed by Medtronic-employed statisticians or designees. A validated statistical software package (e.g., SAS version 9.4 or higher) will be used to analyze the study results.

### 7.2.2. Study Success

As the study objective is to characterize the efficacy and quality of life (QoL) of 3 different amplitude settings, there is no pass/fail criteria proposed to define study success.

### 7.2.3. Urinary Voiding Diary

Symptoms related to overactive bladder (OAB) will be evaluated using paper voiding diaries. Subjects will be trained to complete the urinary voiding diaries for 3 days as part of the baseline and therapy evaluation procedures. The voiding diaries will be completed at baseline, therapy evaluation and prior to the 6 and 12-week follow-up visits.

The value of the relevant data point (UUI episodes [REDACTED]) at each visit will be calculated as the daily average of the available diary days at that visit. Data will be included in the analyses if there is at least 1 day of diary data available at a visit.

### 7.3. Center Pooling

Data from all study centers will be pooled for the analysis. There are no planned statistical methods to test for treatment differences among centers.

### 7.4. Handling of Missing, Unused, and Spurious Data and Dropouts

Missing data imputations will not be performed.

### 7.5. Adjustments for Multiple Comparisons

No adjustments will be made for multiple comparisons because no hypothesis testing will be conducted.

### 7.6. Demographic and Other Baseline Characteristics

Summary statistics will be provided, by randomization group, for baseline and demographic variables for subjects who are randomized, and will include:

- Age
- Sex

[REDACTED]

[REDACTED]

- Body Mass Index (BMI)

[REDACTED]

[REDACTED]

[REDACTED]

### 7.7. [REDACTED]

[REDACTED]

[REDACTED]

[REDACTED]

[REDACTED]

## 7.8. Interim Analyses

No formal interim analysis is planned for this study. Interim descriptive summaries may be performed; however, if provided, the study team, investigators and site personnel will be blinded to this information. No study decisions will be made from descriptive summaries; therefore, no sample size adjustment is needed.

## 7.9. Evaluation of Objectives

### 7.9.1. Primary Objective

To explore the effect of three different amplitude settings (50% of sensory threshold, 80% of sensory threshold, and sensory threshold) on UUI episodes per day. Descriptive statistics for change in UUI from baseline to 12 weeks will be provided in each randomized group.

Negative values for a change from baseline represent an improvement in UUI episodes and positive values represent an increase in UUI episodes.

#### 7.9.1.1. Experimental Design

Experimental design for data collected on the urinary voiding diary is described in Section 7.2.3.

#### 7.9.1.2. Endpoint Success Definition

This objective is to explore and characterize the reduction in number of UUI episodes under each amplitude setting from baseline. There are no pass/fail criteria proposed to define this endpoint success.

#### 7.9.1.3. Analysis Methods

Descriptive statistics including mean, standard deviation, 95% confidence intervals, median, minimum and maximum will be provided by randomization group.

Change will be calculated as the difference between average of daily UUI episodes from follow-up to baseline. This will be calculated for each subject and the average change will be reported with descriptive statistics. UUI episodes will be included in the calculation irrespective of urgency status.

## 7.9.1.4. Analysis Populations and Sensitivity Analyses

The analysis population for this objective will be on the CC population, and subjects will be analyzed according to their randomization assignment for the primary analysis. In addition to the primary analysis, an as-treated (AT) sensitivity analysis will be completed to assess the robustness of results. The AT analysis will be completed on the CC population but will analyze subjects according to the treatment they receive. Subjects must have received a given treatment for > 50% of their time in the study to be analyzed in that treatment group. Groups for the AT analysis will include 50% sensory threshold, 80% of sensory threshold, sensory threshold, and OFF/other treatment.

[REDACTED]

Additionally, reduction in number of UUI episodes per day [REDACTED] will be assessed at 6 weeks on the CC population, according to their randomization assignment, to assess the effect of different amplitude settings over time.

## 7.9.2. Secondary Objective

To explore the effect of three different amplitude settings (50% of sensory threshold, 80% of sensory threshold, and sensory threshold) on quality of life with the ICIQ-OABqol Questionnaire.

Descriptive statistics for the change in all domains of this questionnaire from baseline to 12 weeks will be provided in each randomized group.

### 7.9.2.1. Experimental Design

The ICIQ-OABqol is a robust, patient-completed questionnaire for evaluating QoL in patients with overactive bladder, for use in research and clinical practice.

The subject-completed questionnaire consists of 4 subscales and a single item on urinary symptom interference. The four subscales of Concern (7 items), Coping (8 items), Sleep (5 items), and Social (5 items) are measured on a scale from 0-100 using a range percentile transformation on the summed value from individual listed items. The Health-Related Quality of Life (HRQL) score is a calculated score with a range from 0 to 100 using a range percentile transformation on the summed value from the subscales. A higher score indicates better quality of life for the HRQL and its subscales; a lower score indicates better quality of life for urinary symptom interference.

## 7.9.2.2. Endpoint Success Definition

This objective is to explore and characterize the QoL under each amplitude setting from baseline to 12 weeks. There are no pass/fail criteria proposed to define this endpoint success.

## 7.9.2.3. Analysis Methods

Descriptive statistics including mean, standard deviation, 95% confidence intervals, median, minimum and maximum will be provided by randomization group. The change in each subscale score from Baseline to 12 weeks will be calculated for each subject and the average change across all subjects in each randomization group will be reported.

## 7.9.2.4. Analysis Populations [REDACTED]

The analysis population for this objective will be on the CC subject set, and subjects will be analyzed according to their randomization assignment for the primary analysis.

## 7.9.3. Additional Measures

Additional measures have been added to provide relevant information on parameters of interest in SNM therapy under different amplitude settings and to provide additional information.

### 7.9.3.1. Incidence of Device Related, Therapy Related and/or Procedure Related Adverse Events

The objective of this measure is to summarize device related, therapy related and/or procedure adverse events (AEs). This objective summarizes device related, therapy related and/or procedure related adverse events, by randomization group, in the post-neurostimulator device implant period. Further analysis of AEs and other safety measures is described in Section 7.10.

#### Experimental Design

AEs will be considered as device, therapy, or procedure related if they are classified as possibly, probably, or causally related to the device (lead, neurostimulator, or external study device), study procedure, or therapy delivery by the device (e.g. device stimulation).

## Endpoint Success

This objective is to summarize device related, therapy related and/or procedure adverse events under each amplitude setting throughout the study. There are no pass/fail criteria proposed to define this endpoint success.

## Analysis Methods

Events will be coded and summarized using the Medical Dictionary for Regulatory Affairs (MedDRA). Summaries will be presented as the number of events, the number of subjects who experienced the event, and the percent of subjects who experienced the event. Events will be summarized in the post-neurostimulator device implant period, and subjects will be analyzed by randomization group.

## Analysis Populations

The analysis population for this objective will be on the randomized subject set, and subjects will be analyzed according to their randomization assignment.

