9.5. Randomization and Treatment Assignment

Once the subject meets all eligibility criteria for the study, and has a successful therapy evaluation, site personnel may proceed with the neurostimulator device implant and randomization procedures. If a subject does not meet all eligibility criteria, subjects should be exited and not proceed to the neurostimulator device implant and randomization procedures.

At the time of the device implant, site personnel will obtain randomization for one of the following therapy amplitudes: sensory threshold, 50% of sensory threshold or 80% of sensory threshold. Randomization will be assigned in a 1:1:1 ratio, and stratified by site. Site personnel will obtain the subject's randomization sequence on the Randomization eCRF which will be generated from the database.

The investigator and research staff at the study site will be instructed to keep the subject blinded to their randomization; however, subjects may or may not feel stimulation. The outcome measures in this study are based on the subject's own assessment. Therefore, keeping the subject blinded to their randomization reduces bias in the outcome measurement reporting. [REDACTED]

During the study, subjects will be encouraged to remain in the randomized treatment arm; however, a subject may request to be re-programmed with a different amplitude setting. If this occurs, a protocol deviation will be required and subjects should continue in the study and complete the remaining follow-up visits.

[REDACTED]

[REDACTED]

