11.1. Definitions/Classifications

Any adverse event meeting the definition of: serious, device related, therapy related and/or procedure related as well as all device deficiencies will be considered reportable for this study. The term “investigational device” is part of ISO14155 definitions. The term “investigational device” refers to any device used in the study including market released devices. Adverse events and device deficiencies are defined as follows:

- **Device Related:** An adverse event that results from the presence or performance (intended or otherwise) of the InterStim II System
- **Procedure Related:** An adverse event that occurs due to any procedure related to the implantation or surgical modification of the InterStim II System. The procedure is defined as the lead placement or implant procedure.
- **Therapy Related:** An adverse event related to therapy delivery by device e.g. device stimulation issue (normally therapy-related events resolve when the device is turned off or reprogrammed).

Table 11-1: Adverse Event & Device Deficiency Definitions

Term	General
Adverse Event (AE) (ISO 14155:2011 3.2)	Any untoward medical occurrence, unintended disease or injury, or untoward clinical signs (including abnormal laboratory findings) in subjects, users or other persons, whether or not related to the investigational medical device. NOTE 1 This definition includes events related to the investigational medical device or the comparator. NOTE 2 This definition includes events related to the procedures involved. NOTE 3 For users or other persons, this definition is restricted to events related to investigational medical devices.
Adverse Device Effect (ADE)* (ISO 14155:2011 3.1)	Adverse event related to the use of an investigational medical device. NOTE 1 This definition includes adverse events resulting from insufficient or inadequate instructions for use, deployment, implantation, installation, or operation, or any malfunction of the investigational medical device. NOTE 2 This definition includes any event resulting from use error or from intentional misuse of the investigational medical device.

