### 7.10. Safety Evaluation

In the study, all serious, device related, therapy related, and/or procedure related AEs, and all device deficiencies (DDs) are considered as reportable for this study. All reportable AEs and DDs will be summarized. AEs will be considered device, therapy, or procedure related if they are classified as possibly, probably, or causally related to the lead, neurostimulator, external study device, study procedure, or therapy delivery by the device (e.g. device stimulation).

AEs and DDs, referred to as “events” within this section, will be summarized separately. Events will be coded and summarized using the Medical Dictionary for Regulatory Affairs (MedDRA). Summaries will be presented as the number of events, the number of subjects who experienced the event, and the percent of subjects who experienced the event. For AEs, these summaries will be reported for serious adverse events (SAE) as well.

AEs and DDs will be summarized by study phase ( [Redacted] Post-Neurostimulator Device Implant) with the denominator corresponding to the number of subjects in each phase, as described in Section 7.10.7. Events that occur post-neurostimulator device implant will be summarized by randomization group, and overall.

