### 7.10.7.3. Post-Neurostimulator Device Implant

Events that have an onset date on or after the day of the neurostimulator implant procedure will be summarized as Post-Neurostimulator Device Implant Events. Events that occur post-neurostimulator device implant will be summarized by randomization group [REDACTED]

[REDACTED] The [REDACTED] denominator for the summary by randomization group will be the randomized subject set.

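### Post-implant adverse events are tied to amplitude only through the randomised arm; a supplementary table by setting at onset would be a cheap improvement

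*SAP*

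**What the plan says.** **Aim.** SAP 7.9.3.1 (Endpoint Success) describes the measure as a summary of related adverse events "under each amplitude setting throughout the study". Protocol 13.4 also frames it by amplitude setting.

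**Grouping.** The rest of SAP 7.9.3.1 groups by assignment. Under Analysis Methods: "Events will be summarized in the post-neurostimulator device implant period, and subjects will be analyzed by randomization group". Under Analysis Populations: "The analysis population for this objective will be on the randomized subject set, and subjects will be analyzed according to their randomization assignment". SAP 7.10 repeats this: "Events that occur post-neurostimulator device implant will be summarized by randomization group, and overall". SAP 7.10.7.3 fixes the denominator: the "denominator for the summary by randomization group will be the randomized subject set".

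**Changes of setting.** Protocol 9.5 encourages subjects to stay in their arm but accepts that "a subject may request to be re-programmed with a different amplitude setting". That is recorded as a deviation, and the subject continues through the remaining visits. Protocol 7.1 lets the subject switch the device off or lower the amplitude where safety calls for it.

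**Nature of the events.** Protocol 11.1 ties therapy-related events to stimulation being delivered and adds that "normally therapy-related events resolve when the device is turned off or reprogrammed".

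**Efficacy, by contrast.** SAP 7.9.1.4 adds an as-treated sensitivity analysis of the primary endpoint: "Groups for the AT analysis will include 50% sensory threshold, 80% of sensory threshold, sensory threshold, and OFF/other treatment". Protocol 13.3.5 plans an as-treated analysis for quality of life. No readable section plans anything similar for adverse events.

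**The concern.** The randomised arm stands for the amplitude setting only while nobody changes setting. The plan foresees changes in both directions. Protocol 10.1 warns that symptom relief may be less than desired because of the amplitude setting, which gives subjects in a low arm a reason to ask for more. Discomfort gives others a reason to turn down or off.

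For efficacy the plan responds with as-treated groups, including one for OFF/other. For therapy-related adverse events, where the setting at onset is the natural exposure, the readable text offers only the assigned arm. Less uncomfortable stimulation is one of the possible effects of lower amplitude named in Protocol 4.1, so readers will look to this table for a relation between amplitude and tolerability. Events that begin after a change of setting would blur it.

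**Working it through.** **1. Arm size.** Inputs from SAP 6: 42 subjects with 12-week data, 10% attrition, 80% therapy evaluation success, about 48 randomised, about 60 enrolled. Allocation is 1:1:1 (Protocol 9.5).

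- 42 / (1 − 0.10) = 46.7, rounded up to 47; the plan states about 48, which agrees closely.
- 48 / 0.80 = 60, as stated.
- 48 / 3 = 16 per arm; 42 / 3 = 14 per arm among completers.

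The point changes no sample size or precision figure.

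**2. Weight of one subject.** The safety denominator is the randomised set, so one subject is 1/16 = 6.25 percentage points of an arm (1/14 = 7.1 points if only 14 were randomised to it).

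**3. What one or two misplaced subjects do.** The counts are assumptions.

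- Two subjects in the 50% arm are reprogrammed to sensory threshold and then report uncomfortable stimulation. The table shows 2/16 = 12.5% for the 50% arm, with no event at that setting.
- Four of 16 in an arm have an event, so the table shows 4/16 = 25.0%. If one of the four began at another setting or OFF, the share with an event at the assigned setting is 3/16 = 18.75%; if two did, it is 2/16 = 12.5%.

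**4. Effect on a difference between arms.** Assume true rates of 5% at a low setting and 25% at a high one, and let k of 16 subjects change setting before any event. Each then has the rate of the new setting.

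- Low-arm rate = ((16 − k) × 5% + k × 25%) / 16.
- Difference if only the low arm switches = 20 × (1 − k/16) points.
- Difference if k switch in each direction = 20 × (1 − 2k/16) points.

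| k | Low-arm rate | Difference, one-way | Difference, two-way |
|---|---|---|---|
| 0 | 5% | 20 | 20 |
| 1 | 6.25% | 18.75 | 17.5 |
| 2 | 7.5% | 17.5 | 15 |
| 4 | 10% | 15 | 10 |

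The difference shrinks. In the two-way case it reaches zero only at k = 8, half of each arm.

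**5. Whether the existing as-treated rule would serve.** SAP 7.9.1.4 assigns a subject to the treatment received for more than half the time in the study. Take a subject at sensory threshold who has an event in week 1 and is reprogrammed at the end of that week. Over 12 post-implant weeks, 11/12 = 91.7% of the time is at the new setting (11/16 = 68.75% if all 16 study weeks count). The rule would charge the event to the setting adopted because of it.

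**6. Data available.** Event dates are required (Protocol 11.2). Programming data are collected at the implant visit and at every scheduled and unscheduled follow-up visit (Protocol Table 9-1). The documents do not say that changes a subject makes between visits are dated.

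**The case against.** The other side has several good points.

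- **The randomised-arm table is sound.** Grouping by assignment preserves the randomised comparison, and even for efficacy the as-treated analysis is only a sensitivity analysis. A reader might infer that conclusions on tolerability should move to a table by delivered setting. The documents do not support that: changes of setting would depend on tolerability and efficacy, so such a table is open to selection.
- **The commonest sequence may already be right.** If discomfort at the assigned setting leads to a reduction, the event arose in that arm and is counted there. Percentages are per subject, so later event-free time does not remove it. Misplacement needs the change first and the event afterwards.
- **Changes are discouraged and visible.** Off-arm programming is a deviation, deviations are listed and summarised (SAP 7.1.2), and amplitude is reset to the assigned percentage at the 1-week and 6-week visits.
- **Redaction.** SAP 7.7, 7.9.3.2, 7.9.3.3, 7.10.1, 7.10.4, 7.10.6 and part of 7.10.7.3 are blacked out, so a summary by setting there cannot be excluded.
- **Stakes are limited.** Safety is an additional measure, there is no hypothesis testing, and the protocol synopsis says the sample is too small for comparisons between groups.

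These points limit the size of the gap and the reach of any fix. They do not close it. The text of SAP 7.9.3.1 on aim, methods and population is readable, and it states an aim by amplitude setting with a grouping by assignment only.

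**Conclusion.** The point holds as a cheap improvement. In the readable text, post-implant adverse events are related to amplitude only through randomisation assignment, while subjects may move to another amplitude or OFF and remain in follow-up. Therapy-related events that start after such a move are charged to a setting not being delivered, at 6.25 percentage points per subject with 16 per arm. The likely effect is to weaken an amplitude-tolerability pattern, on the assumption that event risk follows the delivered setting.

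The total effect cannot be stated, because the documents give neither a switch rate nor an event rate; the figures above are illustrations. A reader might infer that the pattern could be reversed. Nothing in the documents supports that: in the two-way illustration, more than half of both arms would have to switch before any event.

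**What to change.** In SAP 7.9.3.1 and 7.10.7.3:

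- Keep the table by randomised arm as the main summary.
- Add a supplementary table or listing of device- and therapy-related post-implant events by the last programmed setting recorded before onset: 50%, 80%, sensory threshold, OFF/other.
- Give approximate time at each setting from visit programming data where available.
- Do not use the more-than-half-the-time as-treated rule for this table.
- Leave procedure-related events by randomised arm.
- State that the added table is non-randomised, may miss changes subjects make between visits, and supports interpretation without replacing the randomised summary.

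The cost is a short SAP paragraph and one table or listing, built from event dates and visit programming data already collected. Exact time at each setting may not be obtainable; if so, the listing alone is enough.
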